Recruitment. Eligible participants will contact our study in response to 1) flyers posted in VA mental health, primary care, and alcohol and substance use treatment programs; 2) advertisements in print and web-based media; 3) referrals from VA primary care, SAMI, PTSD, and other psychiatry clinics and 4) from other research studies who's participants provided consent to contact. Following verbal consent, potential participants will undergo an initial screening that takes approximately 30-45 minutes to complete. The screening, used in the PI's current CSR&D merit study, is intended to detect clinically significant alcohol use and PTSD symptoms. It consists of screening items from the SCID [52] and the Posttraumatic Stress Disorder Checklist-5 [PCL-5; 53] for disorders that are part of the inclusion and exclusion criteria. Those who meet study criteria will attend an in-person interview where they will sign informed consent documents and take part in a baseline assessment (see measures in 9.8.). Following baseline assessment, participants will have the opportunity to meet with a research study therapist to talk about their goals for taking part in the study treatments and the pros and cons of taking part in the study. Following the session, participants who choose to proceed with study participation will be randomized to the intervention or control condition. Random permuted blocks will be used which ensure exactly equal treatment numbers at certain equally spaced points in the sequence of patient assignment. A computer-generated randomization sequence will be provided by our and held by [name] study pharmacist. *Randomization will be stratified by whether or not the participant is on a anti-relapse medication. It is expected that randomization will balance out severity of PTSD symptoms, severity of alcohol use, and functional impairment, and this will be assessed in analyses excluded.*

Women and Minorities

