Standard Pharmacotherapy. Pharmacological treatment will be provided at no cost to the proposed project. The VA follows treatment guidelines that require standardized prescribing practices for individuals with PTSD, depression, and AUD. We expect at least 85% of

participants will be receiving medications based on these guidelines. We recognize that pharmacotherapy and changes in medications will be an uncontrolled source of variance but expect that any changes will be similar across treatment conditions and thus balanced by randomization. We considered recruiting participants who were not on medication or asking participants to be medication stable prior to study entry. However, psychotropic medications have well documented effectiveness for the treatment of PTSD and withholding such medication would be inappropriate for this high-risk population. The only exception is if participants are on addiction medications they will be asked to stay on a stable approved dose at least two weeks before starting the study drug and throughout the study. Study coordinators will record from VA medical records and patient self-report all treatment (psychotherapy and medication) in which Veterans participate in the VA. Participants will also be asked about treatment outside of the VA. We will compare treatment as usual between our two conditions and, if differences in any variables are found, include these as covariates in analyses.

Blind. All investigators, clinicians, and study staff will be blind to treatment condition. Only the research pharmacist will know to which group participants have been randomized. The success of the blinding procedure will be evaluated by having the rater guess the patient's assigned treatment condition after each assessment. If indicated, participants will be asked to go through detoxification prior to beginning the study. Detoxification programs are available on inpatient and outpatient bases through programs funded by the San Diego VA.

Sources of Materials: The data relevant to the proposed project will be gathered strictly for research purposes. Blood and urine specimens obtained are for clinical and research purposes only. Sources of research data will be demographic data collected from participants recruited for this study, ratings from independent clinical evaluators, patient self-reports, toxicology screens, and through VA CPRS chart review.

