- **Data Management.** In the initial 3 months, data management procedures will be developed and implemented. Data entry and quality assurance will be ongoing during enrollment, with validation and double-entry procedures in place to ensure accurate data entry. Study staff will be trained to limit missing data by checking questionnaires

immediately and prompting for additional response and re-contacting participants if necessary. Study staff will attempt to collect all post-randomization data regardless of treatment attrition.

- **Statistical Analysis.** Data analysis will occur in a staged approach, moving from initial descriptive analyses to hypothesis tests. Descriptive statistics and plots will summarize and assess distributional properties of key variables. Randomized groups will be compared on baseline demographic and clinical variables using analysis of variance, 2, or Wilcoxon-rank sum tests. Any baseline variables potentially confounded with treatment condition will be incorporated in the primary analyses as covariates. Outliers will be assessed and variables whose distributions depart significantly from normality will be transformed.

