- **Primary Aim Analysis.** As stated in Aim 1, we will evaluate the efficacy of PE+TOP, as compared to PE+PLA, in percent heavy drinking days (PHDD) among Veterans with comorbid AUD/PTSD at post-treatment and 3- and 6-month follow-up. The statistical model will be a generalized linear mixed model with a log link and gamma distribution variance function. If the over-dispersion parameter is close to zero a Poisson regression model will also provide equivalent model fit. The model will include a factor for treatment condition (PE+TOP, PE+PLA) and a linear term for time (baseline, post-treatment, 3, and 6 month follow-up). This model can be expanded to determine an adjusted intervention effect by including covariates such as gender and era of service. The primary test of treatment effect will be a group x time interaction. This flexible analytic method provides maximum likelihood parameter estimates based on all of the available data, allowing for the inclusion of cases with missing data and the modeling of the covariance error structure of the data across the

assessment points [90]. If the extent of missing data is small and the data appear to be consistent with a missing-at-random model, we will also carry out maximum-likelihood based on a “completer-analysis” using the observed data.

- **Secondary Aim Analyses.** As stated in Aims 2 and 3, veterans in PE+TOP, compared to PE+PLA, will show greater improvements in PTSD, depression symptoms, functional impairment and quality of life at post-treatment and 3- and 6-month follow-up. We will first examine the relationships among these outcomes to determine if composite scores should be created from highly correlated variables. This will help to reduce the number of statistical tests. The statistical model for these analyses will be random effects regression models as described in the primary aim analysis section, using identity link for Gaussian distributed linear variables and log or logit link functions for discrete or skewed outcome variables. These analyses would be in an intent-to-treat framework using maximum likelihood as before.

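### Covariates for the primary analysis are picked by testing the randomized arms for baseline differences, which leaves the primary model unfixed and ignores prognostic value; a short prespecified set should replace the rule.

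*Combined protocol and SAP*

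**What the plan says.** All references are to Section 9 (Design and Methods) of the combined protocol and SAP.

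- **Statistical Analysis.** "Randomized groups will be compared on baseline demographic and clinical variables using analysis of variance", or by chi-square or Wilcoxon tests. The next sentence is the selection rule: "Any baseline variables potentially confounded with treatment condition will be incorporated in the primary analyses as covariates". No cut-off, list of variables or other criterion for confounding is given.
- **Primary Aim Analysis.** The fixed terms are few: "The model will include a factor for treatment condition (PE+TOP, PE+PLA) and a linear term for time". Baseline drinking enters as the first time point, and "The primary test of treatment effect will be a group x time interaction". Other covariates are optional and open-ended: "This model can be expanded to determine an adjusted intervention effect by including covariates such as gender and era of service".
- **Recruitment.** "Randomization will be stratified by whether or not the participant is on a anti-relapse medication". The primary model does not list this factor.
- **Standard Pharmacotherapy.** A second rule of the same kind covers concurrent care: "We will compare treatment as usual between our two conditions and, if differences in any variables are found, include these as covariates in analyses".
- **Missing Data.** Covariates related to missingness are called for, but none is named.

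No section replaces the baseline-test rule with a fixed set.

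**The concern.** With valid randomization, every baseline difference between arms is a chance difference, so testing it gives no information about confounding. What makes a baseline variable worth adjusting for is its relation to the outcome, and the rule does not look at that. It can admit a variable unrelated to drinking because it happens to be imbalanced, and it can leave out a strong predictor whose imbalance falls just short of the cut-off.

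Two things are at stake. First, the primary model depends on which variables are tested and at what level, and neither is stated; both can be settled after the arms have been compared. Second, the trial is short of power by its own account: the Power analysis paragraph gives 72% one-sided at N = 120 and says the 192 needed for 80% two-sided cannot be recruited. Precision from prognostic covariates is one of the few gains left that needs no extra participants.

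**Working it through.** **Inputs from the protocol.** d = 0.406 (so SD = 1), N = 120, 60 per arm. The alpha level is not stated; 5% is assumed, and it reproduces the plan's figures.

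**1. The plan's own figures.** For a two-arm comparison the noncentrality is d x sqrt(n/2), with n per arm.
- One-sided, N = 120: 0.406 x sqrt(30) = 2.224; power = Phi(2.224 - 1.645) = 71.9% (71.4% with the t distribution). Stated: 72%.
- Two-sided 80% power at 0.406: N = 192. Stated: 192.
- Two-sided power at d = 0.516, N = 120: 80.7% (normal) or 80.0% (t). Stated: 80%.

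All agree, and none depends on this point.

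**2. How often chance alone changes the model.** With K independent variables each tested at an assumed 5%, P(at least one flagged) = 1 - 0.95^K.

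| K | P |
|---|---|
| 5 | 23% |
| 10 | 40% |
| 15 | 54% |
| 20 | 64% |

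**3. Precision in a single-visit arm comparison.** A fixed covariate with outcome correlation r reduces the residual SD to sqrt(1 - r^2), so the noncentrality becomes 2.224 / sqrt(1 - r^2). The documents give no r; 0.3 to 0.5 is assumed.

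| r | Noncentrality | Power, always adjusted |
|---|---|---|
| 0.3 | 2.331 | 75% |
| 0.4 | 2.426 | 78% |
| 0.5 | 2.568 | 82% |

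Simulation of the same comparison gave 74%, 78% and 82% with the covariate always in the model, and 72% at all three correlations when it entered only if its baseline test was significant. Selection recovers almost none of the gain.

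**4. Type I error of the rule.** In 6,000 simulated trials per scenario, with 10 baseline variables of which one was prognostic, one-sided error under selection was 0.049 at R^2 = 0.1 and 0.036 at R^2 = 0.5. It is at or below the nominal 5%.

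**5. The stated group x time test.** Take a linear random-intercept model, four equally spaced visits (-1.5, -0.5, 0.5, 1.5; sum of squares 5), total SD 1, an assumed intraclass correlation of 0.5, and an effect of 0.406 at each post-baseline visit.
- The slope contrast is 0.406 x (-0.5 + 0.5 + 1.5)/5 = 0.122. The variance of a participant's slope is 0.5/5 = 0.1. Noncentrality = 0.122 / sqrt(0.1 x 2/60) = 2.11, so power is 68%.
- *Covariate related equally to all four visits.* It cancels out of every participant's slope. Power is 68% with or without it.
- *Covariate related only to post-baseline drinking.* It contributes 0.3r to the slope, adding 0.09r^2 to the slope variance if ignored. For r = 0.3, 0.4 and 0.5, unadjusted power is 65%, 63% and 60%; with the covariate x time term it returns to 68%. That is a gain of roughly 3 to 8 points by this approximation, and about 3-7 points in simulation of the fitted model.

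**6. Covariate added as a main effect only.** In the linear model with complete data, the group x time estimate and its standard error do not change. In a gamma log-link marginal model, used as a stand-in for the planned mixed model, the SD of the interaction estimate fell from 0.068 to 0.064 with complete data and from 0.086 to 0.073 with dropout: a modest change.

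**The case against.** The strongest reply is that the rule hardly matters for the test the plan has named. That test is group x time with baseline drinking already in the outcome vector, so a covariate entered additively leaves it unchanged in a linear model and moves it only modestly under a log link. If selected covariates barely move the test, chance selection barely moves it either. This limits the size of the point. It does not justify the rule: a procedure that does little for the primary test and still leaves the model open has nothing to recommend it. The primary analysis also yields estimates beyond that one coefficient.

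A reader might infer that the trial gives away up to 10 points of power (72% against 82%). Those figures belong to the single-visit comparison used for sample size. For group x time the gain needs a covariate that predicts change in drinking, and nothing in the documents shows that any particular variable does.

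A reader might also infer that near-threshold imbalance leaves a false-positive rate of 12-17%. That is a conditional figure: a single-visit comparison, given an imbalance in one direction just below an assumed cut-off. For group x time with a covariate related equally to all visits, error in the same window stayed at about 4-5%; it reached about 10-16% only when the covariate related to post-baseline drinking alone. Averaged over all randomizations there is no inflation.

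Finally, the plan offers gender and era of service without any imbalance condition. That is true, but they are examples of an optional expansion, not a commitment.

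**Conclusion.** The point holds as a fault of covariate selection and prespecification. The plan states a rule that chooses primary-analysis covariates on chance imbalance, and no other section overrides it. The model stays open until the arms have been compared, and the rule recovers almost none of the precision of a fixed prognostic set.

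Size: 40-64% of trials would flag at least one of 10-20 independent variables at 5%. Single-visit one-sided power is about 72% against 74-82%. For the primary group x time test the gain from a fixed set runs from none to about 3-7 points.

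These figures rest on an assumed 5% cut-off, independent baseline variables, correlations of 0.3-0.5 and, for group x time, a linear model with an intraclass correlation of 0.5; the documents give none of these. It would go too far to say that the rule inflates type I error, or that the plan's adjusted effect is not adjusted at all. The second is exact only for an additive covariate in a linear model with complete data; the planned model has a log link and gamma variance.

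**What to change.** 1. Delete the sentence that admits covariates on the basis of baseline comparisons.
2. Name a short covariate set now: the stratification factor (anti-relapse medication, yes/no) plus one or two baseline variables that the team expects, on stated grounds, to predict change in drinking. Gender is a weak candidate on precision grounds, because women were only 10% of the team's current study.
3. Include the set in the primary model whatever the observed balance. Give each covariate an interaction with time in the same coding as the treatment-by-time term: linear if time stays linear, by visit if time becomes categorical.
4. Report the baseline table descriptively, without p-values.
5. Give the unadjusted model as a sensitivity analysis.

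The treatment-as-usual rule under Standard Pharmacotherapy should be looked at separately, since that care may be recorded after randomization.

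The cost is a revision of SAP wording and a few degrees of freedom. Recruitment, visits and data collection do not change. The precision gain for the primary test may be small; the certain gain is a model fixed before the arms are compared.

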10) Describe the characteristics of the proposed subject population. Include age, gender, ethnicity, and health status as appropriate. Provide inclusion and exclusion criteria as appropriate. Indicate the number of VASDHS participants to be studied. For multisite studies, also provide the total number of subjects from all sites. Indicate the estimated number of consented subjects that will fail the screening process, if any.

Protection of Human Subjects

1. Risks to the Subjects.

1.a. Human Subjects Involvement and Characteristics

The participants in this study will be 120 outpatient male and female Veterans (60 per treatment condition), ages 18 or older, with alcohol use disorder (AUD) and PTSD.

In order to ensure that our sample represents the diversity of comorbidity in Veterans with PTSD, exclusion criteria are minimized and include only those factors that contraindicate primary treatment for PTSD, prevent the Veteran from benefiting from the current program, or may interfere with the mechanisms under study.

Inclusion criteria are:

- 1) Veterans of the U.S. military and/or Reserve/National Guard members,
- 2) at least 18 years of age,
- 3) survivors of a psychological trauma meeting DSM-5 criterion A, and are at least one month post-trauma,
- 4) have current DSM-5 diagnoses of AUD and PTSD based on semi-structured diagnostic interviews,
- 5) have at least 20 days of heavy drinking (≥ 5 drinks/day for men and ≥ 4 drinks per day for women) in the last 90 days spent in a non-restricted environment and meet criteria for heavy drinking at least 4 days in the last 30 days prior to screening,
- 6) are not currently receiving trauma-focused psychotherapy,
- 7) are literate in English and intend to stay in the San Diego area during the study,
- 8) are willing to attend psychotherapy, medication, and assessment sessions,
- 9) trying or planning to try to cut down on or abstain from alcohol,
- 10) for females of childbearing potential, agree to use an approved form of contraception for the duration of the study, including hormonal contraceptives (e.g., oral contraceptives or implantable devices), intrauterine device (IUD), or double barrier methods (e.g., diaphragm with spermicidal condom); barrier method is preferred as topiramate may make birth control less effective,

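### The general rule to transform non-normal variables does not exempt outcomes, so the plan does not fix whether percent heavy drinking days (PHDD) enters the log-link primary model untransformed

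*Combined protocol and SAP*

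**What the plan says.** Three places in the combined protocol and SAP bear on this.

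- **Section 9, Statistical Analysis.** The order of work is stated first: "Data analysis will occur in a staged approach, moving from initial descriptive analyses to hypothesis tests". The descriptive stage is then described: "Descriptive statistics and plots will summarize and assess distributional properties of key variables". The paragraph ends with an assessment of outliers and the rule that "variables whose distributions depart significantly from normality will be transformed". The rule is worded as mandatory and applies to variables in general. PHDD is neither named nor exempted.
- **Section 9, Primary Aim Analysis.** The outcome is PHDD, with no mention of a transformed version. The model is a "generalized linear mixed model with a log link and gamma distribution variance function", with Poisson regression mentioned for the case of little over-dispersion. The primary test is the group by time interaction.
- **Section 9, Secondary Aim Analyses.** Non-Gaussian outcomes are handled by "log or logit link functions for discrete or skewed outcome variables".

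Two eligibility criteria in Section 10 shape the distribution of PHDD. Criterion 5 requires that participants "have at least 20 days of heavy drinking" in the last 90. Criterion 9 admits people who are trying, or planning to try, to cut down or abstain.

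**The concern.** The plan holds two remedies for non-normality and does not say which applies to an outcome that has its own model. One changes the observations before analysis. The other leaves them alone and puts the skewness into the link and variance function.

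They do not combine without changing the estimand. A log link on untransformed PHDD gives a ratio of mean PHDD, which is what Aim 1 and Hypothesis 1 ask about. A log link on g(PHDD) gives a ratio of means of g(PHDD), and that is not a ratio of heavy drinking days.

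The choice of g is also open. It would be made after a descriptive stage that, in the same paragraph, compares the randomized groups at baseline, and no text says the choice is made blind to group. Neither model needs the raw variable to be normal: the GLMM does not assume it, and a Gaussian model assumes it of the random effects and residuals. The screen therefore gains nothing for PHDD and leaves an avoidable choice in the primary analysis of a 120-person trial.

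**Working it through.** **1. The plan's own figures.** The plan gives no number for the transformation rule. Its PHDD power figures come from a two-sample t-test. With alpha 0.05 (assumed, since it is not stated) and a normal approximation they reproduce:

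- Two-sided, 80% power: n per arm = 2 × (1.960 + 0.842)² / 0.406² = 95.2, so 96 per arm and 192 in total.
- One-sided, 60 per arm: 0.406 × √(60/2) − 1.645 = 0.579, so power is 71.9%, stated as 72%.
- Two-sided, d = 0.516: 0.516 × √(60/2) − 1.960 = 0.866, so power is 80.7%, stated as 80%.

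These are sound on their own terms but do not settle the scale of the primary effect.

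**2. Would PHDD trigger the rule?** The entry floor is 20/90 = 22%. Follow-up PHDD is bounded below at 0. The plan gives neither a test nor an abstinence rate, so both are assumed: Shapiro-Wilk at 0.05, N = 120, and beta-binomial counts over 90 days with a range of means and spreads.

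| Setting | Samples rejected |
|---|---|
| Baseline, with the 20/90 floor | about 10% to 100% |
| Follow-up, no added abstainers | about 5% to 100% |
| Follow-up, 10% added abstainers | 75% to 100% |
| Follow-up, 20% or 30% added abstainers | 100% |

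Rejection is likely once there is a group of abstainers. It is not guaranteed, and the baseline floor alone does not guarantee it.

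**3. What the coefficient would mean.** Suppose the drug multiplies PHDD among drinkers by 0.75 and leaves the share of abstainers unchanged.

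- Untransformed: ratio 0.75.
- Square root: E√(0.75x) / E√x = √0.75 = 0.866, whatever the distribution or share of zeros.
- log(x+1), PHDD in percent: 0.92 to 0.93 over the assumed shapes. For one drinker at 40%, 0.75 × 40 = 30 and ln 31 / ln 41 = 3.434 / 3.714 = 0.925.
- log(x+1), PHDD as a proportion: about 0.78 to 0.79. For the same drinker, ln 1.30 / ln 1.40 = 0.262 / 0.336 = 0.78.
- Arcsine square root: 0.81 to 0.84.

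In a different assumed scenario, where abstinence also differs between arms (mean PHDD 38.2 against 27.1), the ratio is 27.1 / 38.2 = 0.71 untransformed, 0.77 after square root, 0.80 after log(x+1) and 0.75 after arcsine square root. The plan names none of these transformations.

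**4. Power.** This check used a single time point, 60 per arm, a one-sided test, a ratio of 0.75 among drinkers and 10% to 30% abstainers in both arms. Power was 50-74% untransformed, 26-51% after square root and 14-32% after log(x+1) in percent. Type I error stayed near 5%.

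**5. Where the loss stops.** If the drug acted only by raising abstinence, any transformation with g(0) = 0 would give the ratio (1 − p_T)/(1 − p_P), where p_T and p_P are the abstinent shares on topiramate and placebo. That is the same as on the raw scale, so there is no attenuation. In the 38.2 against 27.1 scenario, a check with the same kind of test showed attenuation of the ratio but no material loss of power. The power loss in step 4 therefore belongs to effects that reduce heavy drinking without abstinence.

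**The case against.** The strongest reply is that the specific text governs the general. The transformation sentence sits in a data-screening paragraph. The Primary Aim Analysis names PHDD as the outcome, fixes its link and variance function in advance, and says nothing about transforming it. A log-link gamma model is chosen because the outcome is not normal, so normalising first would be pointless. The secondary-outcome text points the same way. This is a reasonable reading and probably the intended one. But the plan does not state it, and the screening rule is mandatory and unqualified, so an analyst who followed the document literally would have grounds to transform.

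Three stronger readings are tempting and are not supported:

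- **PHDD must fail the normality screen.** No test or threshold is named, and simulated rejection runs from about 5% to 100%, depending on assumed shape and abstinence.
- **The primary effect will be on a twice-transformed scale picked from the data.** A log link models the log of the mean and does not transform observations. The link and variance function are pre-specified, so only the added transformation would be data-driven.
- **Outlying outcome values will be removed.** The text says only that outliers are assessed.

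It is also fair to say that 0.87 is simply √0.75, that the log(x+1) figure depends on whether PHDD is held in percent or as a proportion, and that the calculations compare arms at one time point. The planned group by time interaction was not simulated. These limits stand, and the figures are illustrations.

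**Conclusion.** The point holds as an unresolved conflict between a general rule and a specific model. The plan does not say that outcomes analysed by GLMM are exempt from the transformation rule, so the scale of the primary effect is not fixed in advance. If the rule were applied to PHDD, the coefficient would cease to be a ratio of heavy drinking days and would depend on a transformation chosen after the data were seen. Under the assumed distributions with 10% or more abstainers, and a drug effect among drinkers only, it would also be attenuated (0.75 to 0.87 or about 0.93, in percent units) and would lose power. The loss would be small or absent if the effect came mainly through abstinence. A reader might infer that the plan requires a transformed primary outcome. It does not go that far, because the Primary Aim Analysis can be read as overriding the screen. The matter is worth settling before unblinding.

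A linked point affects the remedy. A gamma likelihood is undefined at PHDD = 0, while the same paragraph promises maximum likelihood estimates. The remark about Poisson as the low over-dispersion case would fit a Poisson-gamma mixture, that is, a negative binomial, which does admit zeros. The wording does not say that this is meant. Telling the analyst to leave PHDD untransformed is therefore not enough unless the variance function is also settled.

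**What to change.** Amend the SAP text in three places before the blind is broken:

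1. **Statistical Analysis.** Limit the transformation rule to descriptive displays and covariates.
2. **Primary and Secondary Aim Analyses.** State that PHDD and every other outcome analysed by GLMM enter untransformed with the stated link and distribution, and that fit is judged on model residuals.
3. **Primary Aim Analysis.** Replace the gamma wording with a log-link variance function that admits zeros, such as negative binomial, Tweedie or quasi-Poisson. Negative binomial applies most naturally to the count of heavy drinking days, with log days observed as an offset. Negative binomial and Tweedie have a likelihood and so fit the planned missing-at-random maximum likelihood approach. Quasi-Poisson does not, and would need its own statement on missing data.

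The cost is a few sentences. No change is needed to data collection, sample size or conduct.
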